### 7.6.2. Treatment Administration

Subjects will be instructed to apply a small amount of gel [approximately 20-30 mg CLS006 (equivalent to 0.025-0.0375 mg of furosemide)] to cover each wart identified at baseline once daily for 6 weeks (42 consecutive days). Subjects will be instructed to gently rub the gel into each wart for approximately 20 seconds or until the gel is fully absorbed.

Subjects (or caregivers) will apply study drug to each “Baseline Treatment” wart one time per day for the entire treatment period or until instructed to stop by study personnel.

- \* If clinical clearance of a wart is determined **by the PI or an appropriately qualified Sub-I**, subjects should be instructed to stop applying study drug to that specific “wart” (spot) only.
- Merging/Confluent warts should be treated with a small amount of study drug to cover the merged/confluent wart.
- Cluster/Satellite (Splitting) warts should be treated with a small amount of study drug to cover the area (to the outermost wart) considered part of the wart cluster/satellite.

#### **7.6.2.1. Subject Dosing and Use Instructions**

Prior to the first application of study drug, subjects and/or caregiver(s) will be given a copy of the study drug application instructions and study diary for review. The study coordinator or designee should instruct the subject and/or caregiver(s) on proper study drug application and diary completion.

The first application of study drug and documentation of treatment in the study diary will be performed by the subject and/or caregiver(s) under the supervision of the study coordinator or designee as a means of confirming proper study drug application technique and completion of the study diary (refer to Appendix A for detailed instructions).

Thereafter, subjects and/or caregiver(s) will apply at home the daily dose of study drug to the “Baseline Treatment” warts once daily for 6 weeks or until instructed to stop by study personnel. The subject and/or caregiver(s) will be asked to choose a similar time each day, based on convenience, to apply the study drug (e.g., in the morning after showering or in the evening prior to bedtime). Subjects and/or caregiver(s) will be instructed to record the date of each study drug application in the study diary provided.

The study drug should not be applied more than one time per day.

#### **7.6.2.2. Treatment Compliance**

Study drug treatment compliance will be assessed based on the subject’s and/or caregiver(s) reported number of treatment applications. The subject and/or caregiver(s) should record the date of each study drug application in his/her study diary.

Site personnel should review and/or discuss treatment compliance with subject and/or caregiver(s) since last visit based on the completed study diary and/or verbally reported information. Any missed applications should be documented in the source documents (i.e., by subject in the study diary or by site personnel in subject chart). If compliance is an issue, site personnel should re-instruct subject and/or their caregiver(s) on study drug dosing, application and diary completion, as appropriate.

#### **7.6.3. Treatment Assignment**

Prior to the start of the study, a randomization list will be generated by the CRO responsible for biostatistics in the trial. Once it has been established that subjects are eligible to participate in this study, eligible subjects will be randomized within each age group strata ( $\geq 2$  to  $< 12$ ,  $\geq 12$  to  $< 18$  or  $\geq 18$ ) for each study center and assigned a randomization number corresponding to one of two treatment groups in a 1:1 ratio.

#### **7.6.4. Blinding**

This study will be performed in a double-blind fashion. The investigator, study staff, subjects, sponsor, and monitor will remain blinded to the treatment until study closure. The investigational drug and its matching placebo are indistinguishable.

### **7.6.5. Packaging**

Study drug will be provided in 3-gram tubes and packaged into individual subject kits for use by a subject for the duration of the treatment period. Each kit will be numbered with a unique number according to the randomization list generated. Each tube within the kit will be labeled with the matching kit number to correlate with the contents of the kit according to the randomization list generated.

Prior to the start of the study, a randomization list assigning kit numbers to one of two treatment groups in a 1:1 ratio will be generated by the study biostatistician. The drug packaging company will use this randomization list to package study drug into treatment kits.

### **7.6.6. Labeling**

Study drug tubes and kits will be labeled in a blinded manner in accordance with applicable regulatory requirements of the country where the clinical trial will be conducted.

### **7.6.7. Unblinding a Subject**

Study drug supplies will be packaged in a manner supporting the blinding of the study.

Unblinding a subject's treatment assignment should ONLY be performed in an emergency, when knowing the identity of a subject's assigned treatment is essential to their continuing medical care. If at all possible, every attempt should be made to contact the Medical Monitor/Safety Contact to discuss before unblinding. In the event of unblinding, the Medical Monitor/Safety Contact and/or Project Manager must be notified immediately (within 24 hours (1 business day)), and the circumstances under which the blind for a given subject was broken must be appropriately documented in the source documents.

### **7.6.8. Dispensing and Return of Study Drug**

Each eligible subject will be assigned a kit from those available at the site according to the randomization schedule using the Interactive Web Response System (IWRS). When the kit is assigned, study personnel must record the required information on the kit and tube labels and attach the label(s) to the appropriate source document. The kit assignment must be recorded in the source document.

From the subject's assigned kit, one tube of study drug will be dispensed to the subject and/or caregiver(s) from his/her assigned study drug kit at Baseline, and again at his/her Week 2 and 4 visits. One extra tube will be in the kit in the event it is needed (e.g., tube is lost). Tube dispensation and return must be recorded in the source document.

The subject and/or caregiver(s) will be instructed to return the tube of study drug at each study visit. At the Week 2 and 4 Visit, the used tube will be exchanged and a new tube of study drug will be dispensed from the subject's kit.

### **7.6.9. Accountability**

In accordance with federal regulations, the Investigator must agree to keep all clinical supplies in a secure location with restricted access.

Upon receipt of the clinical supplies, the Investigator or designee will conduct a complete inventory of all study drug and assume responsibility for storage and dispensing. Dispensation and return of study drug must be appropriately documented. Under no circumstance should any of the clinical supplies sent to the Investigator be used in any unauthorized manner.

All used and unused clinical supplies will be appropriately inventoried and returned to the designated facility as specified by the Sponsor.

### **7.6.10. Prior and Concomitant Medication/Treatment**

Prior and concomitant medication/treatment history will be collected at Screening and reviewed/updated at the Baseline visit. Medications/Treatments used within 1 month prior to the Baseline visit and any washout medications/treatments specified (refer to Section 7.6.10.1) should be appropriately documented in the source documents. Wart treatments used within the last year should be recorded.

Any medication/treatment used by the subject either at or following the Baseline visit through study completion will be considered concomitant medication/treatment (e.g., aspirin, Tylenol, birth control pills, vitamins). Every attempt should be made to keep concomitant medication/treatment dosing constant during the study. Any change to concomitant medication/treatment should be appropriately documented in the source documents.

An AE should be recorded for any subject starting a concomitant medication/treatment (except medications/treatments used as prophylaxis) to treat any health condition/event not identified in the subject's medical history.

#### **7.6.10.1. Excluded Concomitant Medication/Treatment**

Other than the study drug, no other treatment, product, or therapy (prescription or over-the-counter) intended for the treatment of warts is permitted during the course of the study including the follow-up period, according to the instructions listed below.

The following treatments/medications are prohibited in the treatment area during the study including:

- Use of any wart treatments/therapies, prescription or over-the-counter products as follows:
  - \* Salicylic acid, cantharidin, simple occlusion (e.g., duct tape), and/or any other over-the-counter wart-removing products in the treatment area.
  - \* Cryotherapy (e.g., treatment with liquid nitrogen), carbon dioxide, electrodesiccation, laser, surgery, or other forms of mechanical destruction (e.g., emery boards, clippers, debriders, etc.) in the treatment area.

The following treatments/medications are prohibited in the treatment area and/or outside the treatment area during the study, including the follow-up period:

- Use of systemic immunosuppressive or immunomodulatory medication (including oral or parenteral corticosteroids) during the course of the study.
  - \* Routine use of inhaled or intranasal corticosteroids during the study is allowed;
- Treatment with immunotherapy (DPCP, DNCB or other), imiquimod, 5-fluorouracil, bleomycin, podophyllin or any other wart immunotherapy or treatment designed to stimulate immune response.
- Use of sinecatechins (VeregenTM)
- Use of topical and/or systemic Isotretinoin (e.g. Accutane).
- Ongoing treatment with cimetidine or other H2 receptor antagonists.
- Ongoing use of oral or injectable furosemide during the course of the study.
- Use of an investigational drug/device and/or participation in another investigational study.

## 7.7. STATISTICAL METHODS PLANNED

### 7.7.1. General Considerations

A Statistical Analysis Plan (SAP) will be developed and finalized prior to unblinding of the study. The SAP will include detailed methods of analysis, algorithms for handling data, any deviations from the protocol methods, and mock data displays.

### 7.7.2. Sample Size Determination

The sample size estimates for the current study are based upon the rates of clearance of warts in the previous Phase 2 study [REDACTED]. This was a randomized, double-blind, vehicle-controlled, Phase II study in 80 subjects who were treated with topical [REDACTED], furosemide, [REDACTED], or vehicle for 42 days daily with an 8-week follow-up period. For the furosemide treatment group, the proportion of subjects with all cleared warts was 0.1 (10%) versus 0 in the vehicle.

The difference in the proportion of subjects with all treated warts cleared (complete clearance) at the Week 18/End of Post-treatment Efficacy Evaluation period (is the primary endpoint of the current study. For conservative purposes, assuming 10% and 2% complete clearance rates in the furosemide and vehicle treated groups respectively 200 subjects randomized per treatment group will provide for 92% power at a two-sided  $\alpha$  of 0.05 to detect a difference between active and placebo.

With the inclusion of an additional 80 subjects in the  $\geq 2$  to  $< 12$  cohort, the total sample size of 480 will provide 96% power with the assumption unchanged.

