## **7. INVESTIGATIONAL PLAN**

### **7.1. OVERALL STUDY DESIGN**

This study will be conducted in accordance with the FDA and ICH guidelines on current GCP, following the ethical principles originating from the Declaration of Helsinki. Additionally, the study will be conducted in accordance with any applicable laws or regulations of the country in which the clinical research is conducted.

The study will be conducted as a randomized, double-blind, vehicle-controlled, parallel group, multicenter study at approximately 40 sites involving approximately 480 subjects (~240 per treatment group) with nongenital cutaneous common warts. Approximately 160 of subjects enrolled will be pediatric subjects, (~80 will be  $\geq 2$  to  $< 12$  years of age and ~80 will be  $\geq 12$  to  $< 18$  years of age).

After giving informed consent, subjects will be screened for study eligibility according to the specified inclusion/exclusion criteria. Subjects must be male or female  $\geq 2$  years of age with 1 to 6 clearly identifiable common warts (*verruca vulgaris*) located on hands (dorsal, periungual, or palmar), feet (dorsal), limbs, and/or trunk. Eligible subjects will be randomized and stratified by age  $\geq 2$  to  $< 12$ ,  $\geq 12$  to  $< 18$  or  $\geq 18$ ) and investigative site to one of two treatment groups in a 1:1 ratio (CLS006 or vehicle gel).

Subjects or their caregiver(s) will apply the first application of study drug under supervision at the study site to ensure understanding of the treatment application instructions. Thereafter, subjects or their caregiver will apply study drug at home to all common warts treated at baseline once daily for 6 weeks. The 6-week treatment period will be followed by a 12-week post-treatment efficacy evaluation period. After completion of the 12-week post-treatment efficacy evaluation period, subjects who achieved clearance of at least one treated wart at week 18 will continue into the 12-week follow-up period for evaluation of recurrence and durability of response.

Other than the study drug, no other treatment, product or therapy (prescription or over-the-counter) intended for the treatment of warts is permitted during the course of the study including the follow-up period in accordance with the excluded medications/treatments listed in Section 7.6.10.1.

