### **7.2.3. Discontinuation and Withdrawal from Treatment or Study**

A subject is free to discontinue treatment or withdraw from the study at any time and for any reason, specified or unspecified, without prejudice to his/her medical care by the physician.

Reasons for discontinuation from Treatment or the Study include, but are not limited to, the following:

- Adverse Event
- Lack of Efficacy
- Pregnancy
- Withdrawal By Subject
- Subject Lost To Follow-Up
  - The Investigator will attempt to reach the subject twice by telephone and once by certified letter before considering the subject lost to follow-up. Lost to follow-up discontinuation and actions taken should be appropriately documented and a copy of the follow-up letter maintained in the Investigator's file.
- Physician Decision

- Non-Compliance with Study
- Study Terminated by Sponsor
- Other

All premature discontinuations from treatment or the study must be appropriately documented in the source documents.

All efforts should be made to evaluate subjects not completing the study (e.g., Early Termination Visit procedures performed).

Subjects who withdraw from treatment or the study will not be replaced.

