### 7.7.3. Randomization

Subjects that meet all inclusion and exclusion criteria will be randomized to one of two treatment groups in a 1:1 ratio for each study center according to a predetermined computer-generated randomization code.

Subjects will be randomized to treatment using an IWRS. The randomization scheme will include age stratum at 3 levels ( $\geq 2$  to  $< 12$ ,  $\geq 12$  to  $< 18$  or  $\geq 18$ ) and investigative site.

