### 7.7.5. Handling of Missing Data

The primary method of dealing with missing data is multiple imputations (MI). Last Observation Carried Forward (LOCF) and Baseline Observation Carried Forward (BOCF) will be used as sensitivity analyses.

For the multiple imputations, twenty sets of imputed data will be generated. These will be imputed using SAS Proc MI as shown below.

```
Proc MI NIMPUTE=20 SEED=861879112 ROUND=....111111  
      MINIMUM=....100000 MAXIMUM=....666666;  
      class treat site sex agegrp;  
      var treat site sex agegrp w0 w2 w4 w6 w12 w18;  
      fcs logistic(treat) logistic(site) logistic(sex) logistic(agegrp) reg(w0) reg(w2)  
      reg(w4) reg(w6) reg(w12) reg(w18);  
      run;
```

Where:

treat = study treatment (CLS006, Vehicle)  
site = investigative site  
sex = sex (male, female)

agegrp = age group ( $\geq 2$  to  $< 12$ ,  $\geq 12$  to  $< 18$  or  $\geq 18$ )

w0 = number of warts at baseline (total number to be treated during the study)

w2 = number of remaining treated warts at Week 2

w4 = number of remaining treated warts at Week 4

w6 = number of remaining treated warts at Week 6

w12 = number of remaining treated warts at Week 12

w18 = number of remaining treated warts at Week 18

Note: Variable names may differ from those used in the actual programs, but the methodology will be the same.

If an imputed value is not within the appropriate range after the default of 100 tries, the SAS Proc MI option MINMAXITER may be increased in order to impute appropriate values.

In general, data will not be imputed for safety analysis.

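### The stated 92% and 96% power assume that every randomised subject has an observed Week 18 outcome; with 15 to 20% missing, the 96% becomes about 93 to 91%

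*Protocol*

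**What the plan says.** Protocol 7.7.2, repeated in SAP 6.1, assumes complete clearance at Week 18 of 10% on furosemide and 2% on vehicle, with two-sided alpha 0.05. On that basis "200 subjects randomized per treatment group will provide for 92% power". Eighty further subjects aged 2 to under 12 are then added, and "the total sample size of 480 will provide 96% power with the assumption unchanged". Protocol 7.1 puts the study at about 240 per arm. Neither sample-size section mentions drop-out, evaluable subjects or inflation.

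Elsewhere the plan provides for missing outcomes:

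- Protocol 7.2.3 lists lack of efficacy and loss to follow-up among the reasons for leaving, and says: "Subjects who withdraw from treatment or the study will not be replaced".
- The primary outcome is read at Week 18, 12 weeks after dosing ends.
- Protocol 7.7.4 makes all randomised subjects the primary population.
- Protocol 7.7.5 and SAP 12.5.2 make multiple imputation (20 sets) the primary way of handling missing counts, with LOCF and BOCF as sensitivity analyses.

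**The concern.** The power is stated per subject randomised, while the analysis sections expect some subjects to have no Week 18 count. Imputation keeps those subjects in the denominator but does not restore the information lost. Earlier visits help only in part, and the variation between imputations enlarges the denominator of the pooled statistic.

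Two things are at stake. The stated power is what a reader would use to interpret a negative primary result, and under Protocol 7.7.6.2 and SAP 12.5.3 the primary test gates every secondary test. The rise from 92% to 96% is also credited wholly to the 80 added children, so those subjects cannot serve as an unstated drop-out allowance as well.

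**Working it through.** **Inputs.** From Protocol 7.7.2: p1 = 0.10, p2 = 0.02, two-sided alpha 0.05, and n = 200 per arm, then 480 in total. From Protocol 7.1 and 7.7.3: 1:1 allocation, so about 240 per arm. The drop-out rate is not in the documents. I assume 5 to 25%, completely at random and equal in both arms.

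**Step 1: reproduce the plan's figures.** Two-proportion formula with pooled variance under the null:

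power = Φ{ [δ√n − 1.96·√(2p̄(1−p̄))] / √(p1(1−p1) + p2(1−p2)) }

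Here δ = 0.08 and p̄ = 0.06. Then √(2·0.06·0.94) = 0.3359, times 1.96 is 0.6583, and √(0.0900 + 0.0196) = 0.3311.

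- n = 200: (0.08·14.142 − 0.6583)/0.3311 = 1.429, power 92.35%. Stated: 92%.
- n = 240: (0.08·15.492 − 0.6583)/0.3311 = 1.755, power 96.04%. Stated: 96%.

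Both match with every randomised subject counted as observed. The continuity-corrected formula gives 88.8% and 94.1%, so it is not the one behind the plan.

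**Step 2: the same formula at n = 240·(1 − d).**

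| Missing at Week 18 (assumed) | Observed per arm | Power | Chance of missing the effect |
|---|---|---|---|
| 0% | 240 | 96.0% | 4.0% |
| 5% | 228 | 95.2% | 4.8% |
| 10% | 216 | 94.1% | 5.9% |
| 15% | 204 | 92.8% | 7.2% |
| 20% | 192 | 91.3% | 8.7% |
| 25% | 180 | 89.5% | 10.5% |

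The miss rate is 7.2/4.0 = 1.8 times the complete-data value at 15% missing, and 8.7/4.0 = 2.2 times at 20%. The number observed falls back to 200 per arm at 1 − 200/240 = 16.7% missing, which uses up the whole stated gain from the added cohort. Counting missing subjects as not cleared gives nearly the same power: 92.6% at 15% and 90.9% at 20%.

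**Step 3: the analysis as written.** The primary test is a CMH test stratified by age group and site, after imputation. SAP 12.5.4 pools sites so that each site-by-age stratum has at least one cleared subject, one not cleared, and one in each arm. Expected clearances are 240·0.10 + 240·0.02 = 28.8, so at most about 29 strata can qualify, against 40·3 = 120 with sites left separate.

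Simulations followed SAP 12.5.2: 20 imputations by bounded and rounded regression, the square-root CMH statistic pooled with standard error 1, and rejection at one-sided p ≤ 0.025. The wart-count distribution is assumed, and loss is random and spread over the post-baseline visits. Monte Carlo error is about 1 point.

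| Site handling | 15% missing | 20% missing |
|---|---|---|
| 10 pooled sites (assumed) | 92.8% | 91.4% |
| 8 pooled sites (assumed) | 92.9% | 90.1% |
| 40 unpooled sites | 90.9% | 87.3% |

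Three further unpooled runs gave 89.1 to 91.3% at 15% and 86.4 to 86.8% at 20%. The pooled results agree with Step 2 to within about one point.

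**The case against.** **The consequence is small.** On the plan's own formula, power is still above 91% with 20% missing. That stands, and it is why no larger sample is asked for.

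**The drop-out rates are assumed.** Also true. The documents give none, and that absence is part of the point.

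**Some leavers will have an endpoint assessment.** The schedule's Week 18 visit also covers early termination after Week 6, with wart assessments, and Protocol 7.2.3 asks for every effort to evaluate subjects who leave. This could reduce the missing share or push losses late. With loss confined to Weeks 12 and 18, a pooled-site simulation gives 95.4% at 15% missing and 93.8% at 20%. The loss is then smaller, but complete-data power in that setting is about 97%, so there is still a loss.

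**A stronger reading is tempting.** A reader might infer that power for the written analysis falls to about 91% at 15% missing and 87% at 20%, so that the miss rate reaches three times the implied 4%. The documents do not support this. Those figures come from stratifying on 40 unpooled sites, whereas Protocol 7.7.7 and 7.7.10 and SAP 12.5.4 provide for pooling. The extra shortfall below the simple formula comes largely from leaving pooling out. On the formula behind the plan, 87% is reached only at about 31% missing.

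**Nor do the documents show that the trial is too small.** Keeping the full 96% would take about 283 per arm at 15% missing (240/0.85) or 300 at 20% (240/0.80), but nothing in the plan requires 96%.

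**Conclusion.** The point holds as a correction to the power statement. The 92% and 96% are arithmetically right for subjects with an observed Week 18 outcome, but they are stated for subjects randomised, in a plan that does not replace withdrawals and expects to impute. With 480 randomised, power is about 93% at 15% missing and about 91% at 20%, a loss of roughly 3 and 5 points from the stated 96%, and the type II error is about twice the implied 4%.

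This rests on assumed loss rates, equal and completely random in both arms, and on the planned 10% and 2% clearance rates. The simulated figures also depend on an assumed number of pooled sites, because the SAP gives a pooling criterion but not the final map. Loss that is unequal or related to outcome was not examined.

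**What to change.** Keep the sample size. In Protocol 7.7.2 and SAP 6.1:

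1. Say that 92% and 96% refer to 200 and 240 subjects per arm with an observed Week 18 outcome.
2. State the drop-out rate assumed and its basis.
3. Give the power that follows, for example: *with 480 randomised, power is approximately 93% if 15% of Week 18 outcomes are missing and approximately 91% if 20% are missing.*
4. Confirm those figures for the pooled-site analysis once the pooling rule is fixed.

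The cost is a few sentences in each document and one confirmatory calculation. No subjects, visits or analyses change. The only downside is a slightly less favourable stated figure.
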